	Standard	Modified
	Noncirrhotic/ Child-Pugh A	Child-Pugh B or Child-Pugh C
Starting Dose ^a (Day 0)	5 mg daily	5 mg once weekly
Titration 1 ^b (≥Month 3)	10 mg daily	5 mg twice weekly
Titration 2 ^b (≥6 weeks after Titration 1)	NA	10 mg twice weekly

^a Starting dose based on subject's cirrhosis status and Child-Pugh Score at Screening.

^b Planned titration regimen is shown; however, the titration of dose and/or frequency is dependent on subject tolerability, biochemical response, and/or changes in cirrhosis status or Child-Pugh Score at any time during the study

^c Dosing per the twice weekly schedule must be at least 3 days apart.

With the exception of liver transplant, if a subject experiences a suspected or confirmed clinical outcomes event, the subject should continue the regular visit schedule and continue taking IP as long as the subject has not met any of the criteria for discontinuation outlined in the protocol. Subjects who discontinue IP are expected to be followed through to study closure (or at the discretion of the Sponsor).

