8.3. Additional Secondary Efficacy Endpoints

8.3.1. Time to Event Analyses

The following time-to-event secondary efficacy analyses will compare OCA versus placebo using the ITT population:

- Time to each relevant component of the primary efficacy endpoint
- Time to development of varix/varices
- Progression to cirrhosis
- Time to occurrence of HCC
- Time to liver-related death
- Time to liver-related death or liver transplant
- Time to liver-related death, liver transplant, or MELD score ≥ 15

All additional secondary time-to-event outcomes with the exception of death will be analyzed in the context of competing risks.

For the following secondary endpoints, liver transplant and death will be considered competing risks:

- Time to each relevant component of the primary efficacy endpoint, with the exception of death and liver-transplant
- Time to development of varix/varices

- Progression to cirrhosis
- Time to occurrence of HCC

For the following secondary endpoints, death will be considered a competing risk:

- Time to liver-transplant

For the following secondary endpoints, non-liver-related death will be considered a competing risk:

- Time to liver-related death
- Time to liver-related death or liver transplant
- Time to liver-related death, liver transplant, or MELD score ≥ 15

Competing risk outcomes will be compared and summarized through a cumulative incidence function (CIF). Gray's (1988) non-parametric test will be used to compare the CIFs of the two treatment groups. Hazard ratios and their 95% confidence intervals will be computed following the Fine and Gray model (1999). Fine and Gray's hazard model can be fit in SAS version 9.4 and higher by specifying eventcode option in PROC PHREG.

Progression to cirrhosis will be assessed in the subset of subjects considered noncirrhotic at Baseline using available medical history, clinical, and laboratory assessments as well as baseline transient elastography (TE), where available. Specifically, subjects with no clinical, laboratory, or radiological evidence of cirrhosis at baseline and/or a TE liver stiffness of < 16.9 kPa (Corpechot 2012) will be considered noncirrhotic. Progression to cirrhosis will be assessed by the development of clinical, laboratory, or radiological evidence of cirrhosis and/or when liver stiffness increases to ≥ 16.9 kPa during the study in which case histological progression to cirrhosis should be confirmed by biopsy unless not medically indicated.

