The percentage of noncirrhotic subjects progressing to cirrhosis during the treatment period will also be summarized by treatment group and compared using a Cochran-Mantel-Haenszel (CMH) test stratified by the randomization stratification factor.

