8.6. Multiple Comparisons/Multiplicity

An interim analysis was conducted after 80 events were observed. A group sequential design using the O'Brien-Fleming type alpha-spending function ([Lan 1983](#), [Reboussin 2000](#)) was used to control the overall two-sided 0.05 significance level that is at an information fraction of 0.63 of the total of 127 events, corresponding to an alpha spend of 0.009. The primary analysis will be conducted at 2-sided 0.041 significance level. No interim analysis will be performed based on the updated endpoints and methodology. The primary endpoint analysis for European Medicines Agency (EMA) filing will be conducted at 2-sided 0.041 significance level.

For the final analysis, the hypothesis testing of key secondary analyses will compare placebo and OCA (the key secondary endpoints are stated in [Section 8.2](#)), provided that the primary efficacy endpoint comparison is statistically significant in favor of OCA. If the primary comparison is not statistically significant then comparison of the key secondary endpoints will be considered as supportive or supplemental. If the primary comparison is statistically significant, the key secondary endpoints will be tested hierarchically in the order described in [Section 8.2](#) at a 2-sided 0.041 significance level. All other secondary endpoints will be tested at nominal 0.041 alpha level.

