14. DEVIATIONS FROM PROTOCOL

14.1. Primary Efficacy Endpoint and Analysis

Due in part to high discontinuation rates and requests from sites to close, the decision was made to stop 747-302 early, at approximately 67% information (84 adjudicated Protocol Version 6 endpoints observed). To increase the number of endpoint events and power to detect a difference, the primary efficacy endpoint has been expanded to include:

- Portal hypertension syndromes (hepatorenal, portopulmonary, or hepatopulmonary)
- Progression to decompensated liver disease (for subjects without decompensation at baseline)
- Progression to clinical evidence of portal hypertension without decompensation (for subjects without decompensation or clinical evidence of portal hypertension at baseline).

The primary efficacy analysis remains the stratified log rank test. With the inclusion of additional endpoints that occur earlier in the course of the disease, the log rank test is limited to each subject's first event, which is likely to be an outcome of lesser clinical importance. A win ratio analysis was added as a sensitivity analysis, to allow for a hierarchical comparison of the composite endpoints. The win ratio analysis allows for the comparison of more severe events such as death and liver transplant to be prioritized over the comparison of earlier-stage events such as progression to clinical evidence of portal hypertension.

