Multiple Imputation (Missing Not At Random) Description

The event rate during off-treatment period (after the treatment discontinuation and before the study close-out) is calculated. The survival time during off-treatment period is assumed to follow exponential distribution of calculated event rate. The survival time during off-treatment

period is added to the survival time during on-treatment period for those subjects who require imputation (ie, early terminators). If the total duration is longer than the period from randomization to study close-out, the survival time will be imputed to the study close-out as a censored observation. Otherwise, the survival time will be imputed to the date of event. Multiple imputation is used to impute the survival time by 5000 iterations.

Procedures:

Step	Description
1	From the ADSL dataset restricted to ITT population (ITTFL='Y'), extract patient identifiers (USUBJID), randomization date (RANDDT), randomized treatment (TRT01PN), death date (DTHDT), treatment (TRT01PN) start (TRTSDT) and stop (TRTEDT) date for treatment, study termination date (WTHDRDT), date of last contact (LASTDT), follow-up after treatment discontinued (FUFL), and stratification factors. Sort dataset by USUBJID.
2	From the efficacy analysis dataset (ADTTE), select the primary endpoint event. Select patient identifiers (USUBJID), randomized treatment (TRT01PN), the censoring indicator (CNSR), follow-up length (ADY), and last contact date (ADT). Sort dataset by USUBJID.
3	Identify patients that discontinued study drug (IPDISC='YES') from the ADDS dataset. Retain USUBJID, analysis start date (ASTDT), and IPDISC variables. Sort dataset by USUBJID.

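### The CMH test of the crude percentage progressing to cirrhosis in an undefined treatment period can mislead if time on treatment or follow-up differs between arms (minor)

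*SAP*

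**What the plan says.** SAP section 8.3.1 treats progression to cirrhosis, among subjects noncirrhotic at baseline, as a time-to-event outcome in the ITT population, with death and liver transplant as competing risks. Gray's "non-parametric test will be used to compare the CIFs of the two treatment groups", and hazard ratios come from the Fine-Gray model. Progression is judged by clinical, laboratory or radiological evidence, and/or by liver stiffness reaching 16.9 "kPa during the study in which case histological progression to cirrhosis should be confirmed by biopsy" (with an exception where biopsy is not indicated). The window there is the study.

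The section's last sentence then changes the window: "The percentage of noncirrhotic subjects progressing to cirrhosis during the treatment period will also be summarized by treatment group and compared using a Cochran-Mantel-Haenszel (CMH)". The randomization factor supplies the strata. The sentence sets no common time horizon, no adjustment for person-time and no rule for subjects who stop IP early.

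The SAP does not define the treatment period. The nearest wording is in Appendix A, in the multiple-imputation description, which speaks of the "off-treatment period (after the treatment discontinuation and before the study close-out". By contrast, the treatment period would be time on IP.

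Three other places bear on the point. Section 3: "Subjects who discontinue IP are expected to be followed through to study closure (or at the discretion of the Sponsor". Section 14.1: "Due in part to high discontinuation rates and requests from sites to close, the decision was made to stop 747-302 early". Section 8.6: "All other secondary endpoints will be tested at nominal 0.041 alpha level".

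**The concern.** A percentage counted over a window that ends at a different time for each subject depends on the length of the window as well as on the hazard. If the window is time on IP, a subject who stops at Month 4 and becomes cirrhotic at Month 18 is scored as a non-progressor, exactly like a subject treated for six years without cirrhosis. The CMH test stratifies on the randomization factors and does not adjust for observation time.

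So one section gives two inferential comparisons of the same endpoint, apparently over different windows, and does not say which governs. They could disagree for that reason alone. Progression to cirrhosis is a stated secondary objective (section 2.1.2), and the CMH p-value could be reported as evidence on it.

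**Working it through.** The SAP gives no expected rate, effect size or number of subjects for the cirrhosis comparison, so there is no plan figure to reproduce. The check asks how the stated test behaves when the drug has no effect.

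**Inputs from the document.** Nominal two-sided alpha 0.041 (section 8.6); 1:1 allocation (section 3.2); about 334 subjects enrolled (Clinical Pharmacology Analysis Plan, section 5), so 334/2 = 167 per arm.

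**Assumptions, not in the document.** The same cirrhosis hazard h in both arms: 0.03, 0.06 or 0.10 per year. Exponential treatment stopping at rate d: 0.10 per year in one arm; 0.15, 0.20 or 0.30 in the other. A 6-year cap. Noncirrhotic subjects per arm: 84, 125 or 167 (about half, three quarters or all of 167). Stopping is independent of progression, and competing events are ignored.

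**Step 1, fixed durations.** Crude percentage = 1 − exp(−h × years).
- h = 0.05, 4 vs 3 years: 1 − exp(−0.20) = 18.1% vs 1 − exp(−0.15) = 13.9%.
- h = 0.08, 4 vs 3 years: 1 − exp(−0.32) = 27.4% vs 1 − exp(−0.24) = 21.3%.

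**Step 2, exponential stopping.** Crude percentage = h/(h+d) × [1 − exp(−6(h+d))]. Mean time on treatment, apart from the event, = [1 − exp(−6d)]/d.

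For h = 0.06:
- d = 0.10: 0.06/0.16 × [1 − exp(−0.96)] = 0.375 × 0.617 = 23.1%.
- d = 0.20: 0.06/0.26 × [1 − exp(−1.56)] = 0.231 × 0.790 = 18.2%.

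**Step 3, false-positive rate.** Normal approximation for two proportions (single stratum), critical value 2.0435. For 23.1% vs 18.2% with 125 per arm, the difference is 0.04914, the pooled null SE 0.05123 and the actual SE 0.05114. Then (0.04914 − 2.0435 × 0.05123)/0.05114 = −1.086, which gives 0.139 in favour of the arm that stops sooner, plus 0.001 the other way: 14.0%.

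Results at h = 0.06, 125 per arm, with 4,000 simulated trials per row as a check:

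| Stopping rate per year | Mean years on treatment | Crude % progressing | Rejects (approximation) | Rejects (simulation) |
|---|---|---|---|---|
| 0.15 vs 0.15 | 3.96 vs 3.96 | 20.5 vs 20.5 | 4.1% | 4.1% |
| 0.10 vs 0.15 | 4.51 vs 3.96 | 23.1 vs 20.5 | 6.8% | 6.6% |
| 0.10 vs 0.20 | 4.51 vs 3.49 | 23.1 vs 18.2 | 14.0% | 13.5% |
| 0.10 vs 0.30 | 4.51 vs 2.78 | 23.1 vs 14.7 | 36.3% | 36.2% |

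For stopping at 0.10 vs 0.20, the range over all hazards and sample sizes is 7.4% (84 per arm, h = 0.03) to 26.0% (167 per arm, h = 0.10).

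**Step 4, alternatives in the same simulations.** With 125 per arm and stopping at 0.10 vs 0.20 or 0.30, a log-rank test censored at stopping rejects 3.6% to 4.5% of the time. A CMH test over a common 6-year window with all follow-up counted rejects 3.5% to 4.7%. Both are close to 4.1%, so the excess comes from the unequal window.

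**The case against.** The best defence is that the test hardly matters. It is an addition to a sound competing-risks analysis that already handles unequal follow-up. Progression to cirrhosis is not among the key secondary endpoints in section 8.2, and the p-value is nominal. This stands, and it keeps the point minor.

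Second, the treatment period is undefined. The Appendix A wording belongs to another analysis, and the sentence may loosely mean the double-blind study. On that reading the Month 4/Month 18 example falls away, and so does the clash of windows. A weaker point remains: a crude proportion over the whole study is still lower in an arm with shorter total follow-up.

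Third, a reader might infer that the arms do differ in stopping, or that the test favours OCA. The documents support neither. Section 14.1 and interim SAP section 6.4 report high or higher-than-expected discontinuation without rates by arm. Interim SAP section 6.3 asks the DMC to look for differences in censoring and reports none. With equal stopping there is no inflation, and the 36.3% figure needs a threefold difference in stopping rates.

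Fourth, counting all follow-up has its own weakness. Under section 8.1.1, last contact can come from record review or half-yearly telephone calls, whereas cirrhosis is found by elastography, laboratory tests and imaging. Cirrhosis may be under-detected once visits stop. This stands, and the fix has to deal with it.

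**Conclusion.** The point holds in conditional form and is minor. As written, the CMH test compares crude percentages over an undefined window that most naturally ends when IP stops. If time on treatment, or total follow-up on the looser reading, differs between arms, the test can reject well above 4.1% with no drug effect, nearly always in favour of the arm observed for less time. The figures rest on assumed hazards, stopping rates and numbers of noncirrhotic subjects, and on stopping being independent of progression. Informative stopping could also bias an analysis censored at stopping. The size and direction in this trial cannot be stated from the documents. No primary or key secondary conclusion depends on the test.

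**What to change.** In section 8.3.1:
- Delete the CMH test and name the Gray/Fine-Gray analysis as the only inferential comparison for progression to cirrhosis.
- From that analysis, report each arm's cumulative incidence at prespecified times (for example 2, 4 and 6 years) with the 95% CI of the difference.
- If a crude percentage is kept, label it descriptive and count it over the same study-wide window as the time-to-event analysis.
- Because detection may weaken once contact is only by record review or telephone, also show a version censored at the last visit with a cirrhosis assessment.

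The cost is a few sentences of SAP text and one extra run of a planned analysis, with no new data collection. What is lost is the simple on-treatment p-value.

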8.3.2. Liver Biochemistry Analyses

Analyses of changes in liver biochemistry (gamma-glutamyl transferase (GGT), ALT, AST, conjugated bilirubin, albumin, and INR) at each visit will be compared between treatment groups using a restricted maximum likelihood based mixed-effect model repeated measures (MMRM) with treatment, baseline, visit, visit by treatment interaction and randomization stratification factors to be included in the model. Visits through Month 24 will be included. An unstructured covariance model will be used. If the computational algorithm fails to converge, the following structures will be tested in the order: Toeplitz, AR(1) and compound symmetry (CS). If the model still does not converge, the stratification factors will be dropped from the model one at a time (UDCA followed by bilirubin).

Change from Baseline over time will be analyzed using analysis of covariance (ANCOVA) with change from Baseline as the dependent variable including treatment group and randomization stratification factor as fixed effects and the Baseline values as a covariate. Descriptive statistics of the laboratory values will be summarized by treatment group. The results, change from

Baseline, and percentage change from Baseline values, as well as estimates of least-square means, standard errors, and 95% CIs, will be presented by treatment group. Estimates of the mean difference between treatment groups, the standard error of the difference, and 95% CI of the difference will be presented.

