All statistical tests comparing groups will be conducted at the 2-sided, 0.05 level of significance, unless otherwise specified (eg, the primary efficacy analysis, [Section 8.6](#)). Summary statistics for each treatment group will be presented, as well as 95% CIs comparing groups.

Baseline Definitions

The Baseline value for statistical analyses of quantitative parameters is defined as the mean of all available study evaluations after the subject signs the informed consent and prior to or on the first administration of investigational product, unless otherwise specified. If there is only one evaluation prior to the first administration of investigational product then the available data from this evaluation will be used as the Baseline value.

The baseline value for analyses of lipid parameters is defined as the last fasted evaluation prior to the first administration of IP.

The baseline value for analyses of qualitative parameters (eg, normal/abnormal) is defined as the last evaluation prior to the first administration of IP.

Baseline values defined above will not change regardless if a subject stops taking investigational product and begins taking commercially marketed OCA.

Visit Windows

Visit windows, as provided below, will be established relative to an individual’s Day 0, the date of first administration of investigational product. Analyses will use visit windows defined by relative day, overriding CRF designated visit numbers.

OCA Therapy 3-Month Interval Visit Windows (Days)

Months	Target Study Day ^a	Analysis Window Study Day ^a	
		Low	High
Day 0	1	Closest visit to Day 1, prior to first IP dose ^b	
Month 1	30	2	46
Month 3	90	47	137
Month 6	183	137	227
Month 9	274	228	318
Month 12	365	319	410
...
Month n^b	$\text{round}(365.25/12*n)$	$\text{round}(365.25/12*n) - 46$	$\text{round}(365.25/12*(n+3)) - 47$

Note: Follow-up visits are not included in visits windows.

^a Study day will be calculated from first dose date.

^b For n in three month increments (15, 18, 21, ...).

Partial Dates

If only a partial date is available and is required for calculation, the following standards will be applied:

- Diagnostic Date (eg, PBC diagnostic date)
 - For missing day only – Day will be imputed as the first day of the month (ie, 1).
 - For missing day and month – Day and month will be imputed as the first day of the year (ie, 1 January).
- Start Dates (eg, event date, AE onset date, or start date of medication)

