Moderate - Total Bilirubin > ULN and Albumin ≥ LLN or

Total Bilirubin \leq ULN and Albumin $<$ LLN

Severe – Total Bilirubin $>$ ULN and Albumin $<$ LLN, where baseline values of total bilirubin and albumin are taken to be the average of all pre-dose measurements.

- The CLIF-C ADs is derived using the following formula:

$$\text{CLIF-C ADs} = 10 \times 0.03 \times [\text{Age (years)}] + 0.66 \times \ln[\text{creatinine (mg/dL)}] + 1.71 \times \ln[\text{INR}] + 0.88 \times \ln[\text{WBC (} 10^9 \text{ cells/L)}] - 0.05 \times [\text{sodium (mmol/L)}] + 8.$$

Inverse Probability of Censoring Weighting

The hazard ratio will be estimated using Inverse Probability of Censoring Weighting (IPCW) techniques (Robins 1999). Baseline predictors of both censoring and clinical outcome will be identified in advance. Augmented IPCW estimators described by Robins may be implemented to explore the possible impact of unmeasured confounding. Baseline predictors of both censoring and clinical outcome for the IPCW analysis are:

- Treatment Group: OCA/Placebo
- Age (year) at Screening Visit
- Sex: Male/Female
- UDCA use at Screening Visit: Yes/No
- Liver biochemistry at Baseline (alkaline phosphatase (ALP) (U/L), alanine transaminase (ALT) (U/L), aspartate transaminase (AST) (U/L), total bilirubin ($\mu\text{mol/L}$), albumin (g/L), and platelets)

The post-baseline time-varying covariates are ALP, ALT, AST, total bilirubin, and AE of pruritus with severity of moderate and severe.

To derive the IPCW weights, the patient's follow-up time up until the time of censoring or event occurring will be partitioned into about 10 intervals. The probability of remaining uncensored at the end of each time interval adjusted for baseline variables, and post-baseline time-varying covariates will be estimated using a pooled logistic regression model. To avoid possible extreme values when taking the inverse of the estimated probabilities from the pooled logistic model with both baseline and time-varying post-baseline covariates, the inverse of these probabilities will be stabilized by multiplying the probability of remaining uncensored conditional only on baseline covariates. Once the IPCW weights are derived, the hazard ratio of treatment effect and corresponding 95% CI will be estimated using a weighted Cox regression model with Sandwich estimator to obtain the robust estimate of the variance-covariance matrix of the parameter estimates.

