5. SUBJECTS

The study aimed to enroll approximately 428 subjects. At study end, approximately 334 subjects were enrolled, and approximately 40 consented to the serial PK substudy.

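### If the unstructured MMRM fails to converge, the named fallbacks force one variance on all visits with no robust standard error, so visit-level tests and intervals are miscalibrated wherever residual variances differ

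*SAP*

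**What the plan says.** Section 8.3.2 of the SAP specifies, for changes in GGT, ALT, AST, conjugated bilirubin, albumin and INR, a "restricted maximum likelihood based mixed-effect model repeated measures (MMRM) with treatment, baseline, visit, visit by treatment interaction" and the randomization stratification factors. "Visits through Month 24 will be included". For the primary fit, "An unstructured covariance model will be used", which gives each visit its own variance. On failure, "If the computational algorithm fails to converge, the following structures will be tested in the order: Toeplitz, AR(1) and compound symmetry (CS"). No heterogeneous-variance version is listed, and no type of standard error is stated for the MMRM.

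The visit grid is in Appendix A, Visit Windows: Months 1, 3, 6, 9 and 12, then "For n in three month increments (15, 18, 21" and so on). "Analyses will use visit windows defined by relative day, overriding CRF designated visit numbers".

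The SAP does specify a robust variance elsewhere. The IPCW analysis in Appendix A uses a "weighted Cox regression model with Sandwich estimator to obtain the robust estimate of the variance-covariance matrix". Section 8.3.2 has no counterpart.

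The second paragraph of Section 8.3.2 adds an ANCOVA of change from Baseline. The promise of LS means, standard errors and 95% CIs of the treatment difference stands in that paragraph. Section 8.6 tests all other secondary endpoints at a nominal 0.041. Section 8.7 repeats the liver biochemistry analyses in the baseline disease-stage subgroups.

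**The concern.** The fallback does more than simplify the correlation pattern. Moving from unstructured to Toeplitz, AR(1) or compound symmetry also discards the visit-specific variances, and nothing takes their place. The treatment contrast at each visit then borrows a pooled variance that can be too small at one end of follow-up and too large at the other.

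There is a reason to expect unequal variances here. The model adjusts for baseline, so the residual variance at a visit depends on how strongly that visit still correlates with baseline. If that correlation decays while the raw variance stays the same, residual variance rises with time.

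The trigger is plausible. The unstructured matrix has 45 parameters, six analytes are modelled, Section 14.1 reports high discontinuation rates, and the analyses are repeated in subgroups. The fallback operates fit by fit, so one table could mix analytes whose standard errors come from different variance assumptions. A smaller matter is that Toeplitz and AR(1) treat visits as equally spaced, whereas the first gap is 2 months and the rest are 3.

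**Working it through.** The plan states no SD, power or sample size for the MMRM, so there is no figure to reproduce.

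**Inputs from the SAP.** Months 1, 3, 6, ..., 24 give 9 post-baseline visits. The two-sided level is 0.041, so the critical value is 2.0435. Enrolment is given in Section 5 of the Clinical Pharmacology Analysis Plan ("At study end, approximately 334 subjects were enrolled"), about 167 per arm; the ratios below do not depend on it.

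**Assumptions, not from the SAP.** Raw variance is constant (set to 1). Correlation with baseline, ρ, falls from 0.80-0.90 at Month 1 to 0.5-0.7 at Month 24, linearly or geometrically. Data are complete and standard errors are model-based.

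**Step 1. Covariance parameters with 9 visits.** Unstructured: 9 × 10 / 2 = 45. Homogeneous Toeplitz: 1 + 8 = 9; AR(1) and CS: 2 each. Heterogeneous Toeplitz: 9 + 8 = 17; heterogeneous AR(1) and CS: 9 + 1 = 10 each. The heterogeneous versions are still far smaller than unstructured.

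**Step 2. Ratio of model to true standard error.** Residual variance at visit j is v_j = 1 − ρ_j². A common-variance model uses the mean of the v_j, so k_j = √(mean v / v_j). The actual level of the 0.041 test is 2[1 − Φ(2.0435 k_j)], and coverage of a 95% interval is 2Φ(1.96 k_j) − 1.

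Example, ρ from 0.90 to 0.50, linear: v = 0.190, 0.251, 0.339, 0.421, 0.498, 0.569, 0.635, 0.695, 0.750, with mean 0.483.
- Month 24: k = √(0.483/0.750) = 0.803; level 2[1 − Φ(1.641)] = 0.101; coverage 88.4%.
- Month 1: k = √(0.483/0.190) = 1.595; coverage 99.8%.

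| ρ, Month 1 to Month 24 | Decay | k, Month 24 | Level, Month 24 | Coverage, Month 24 | k, Month 1 |
|---|---|---|---|---|---|
| 0.90 to 0.50 | linear | 0.803 | 0.101 | 88.4% | 1.595 |
| 0.90 to 0.50 | geometric | 0.821 | 0.093 | 89.3% | 1.632 |
| 0.90 to 0.70 | linear | 0.829 | 0.090 | 89.6% | 1.358 |
| 0.80 to 0.50 | geometric | 0.875 | 0.074 | 91.4% | 1.263 |
| 0.80 to 0.60 | linear | 0.885 | 0.071 | 91.7% | 1.180 |
| 0.80 to 0.70 | geometric | 0.924 | 0.059 | 93.0% | 1.100 |

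**Step 3. One baseline slope.** The formula in Step 2 allows a separate baseline slope per visit, but Section 8.3.2 lists no baseline-by-visit term. With a single slope c, approximated by the mean of the ρ_j, v_j = 1 − ρ_j² + (ρ_j − c)². For 0.90 to 0.50 (linear), k becomes 0.795 at Month 24 (level 0.104, coverage 88.1%) and 1.484 at Month 1. For 0.80 to 0.70 it hardly moves (0.921 and 1.096).

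**Step 4. Second method.** Each homogeneous structure was fitted in large samples to an assumed true covariance, and the model variance compared with the sandwich variance. Assumptions: residual SD linear in time; true correlation exchangeable 0.6 or autoregressive 0.85; 0% or 30% dropout by Month 24, independent of outcome. Coverage of nominal 95% intervals:

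| SD ratio, Month 24 / Month 1 | Month 1 | Month 24 |
|---|---|---|
| 0.67 | 90.3-91.2% | 97.7-99.0% |
| 1 | 95.0-95.1% | 93.4-95.3% |
| 1.25 | 97.0-97.3% | 90.1-92.3% |
| 1.5 | 98.4-98.7% | 87.3-90.1% |
| 2 | 99.6-99.8% | 83.2-86.9% |

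At SD ratio 1, the 93.4% is the single case of CS fitted to an autoregressive truth with 30% dropout. The correlations in Step 2 imply SD ratios from √(0.51/0.36) = 1.19 to √(0.75/0.19) = 1.99, so the two methods describe the same region. A sandwich standard error, or a heterogeneous structure that fits the true covariance, gives k = 1.00 and 95.0% at every visit in large samples.

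**The case against.** A reader might infer that the plan uses model-based standard errors, and that on the fallback Month 24 intervals will be too narrow and early ones too wide. The SAP supports neither as fact. It is silent on the type of standard error; model-based is the usual software default, not a stated choice. It gives no visit-specific SDs or correlations, so the direction rests on variance rising with time. Equal variances essentially remove the effect and falling variances reverse it. This objection stands in full and is why the point is conditional. It does not clear the plan, because miscalibration in the other direction is still miscalibration.

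The consequences are also limited. The fallback may never be triggered. The endpoints are additional secondary ones at nominal alpha, outside the hierarchy, with six analytes at nine visits already unadjusted. The ANCOVA in the same section, if fitted visit by visit, has its own residual variance at each visit. All of this stands and bears on severity. The ANCOVA is only a partial answer, because the SAP does not say that it is fitted by visit or which of the two analyses governs.

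It would also be wrong to claim a specific loss of power at early visits, because the plan sets no power for these endpoints.

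**Conclusion.** The point holds as a minor, conditional weakness. If the unstructured fit fails and standard errors are left at the model-based default, the named fallbacks give miscalibrated visit-level inference wherever residual variances differ.

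Under the assumed fall in correlation with baseline (0.80-0.90 to 0.5-0.7, constant raw variance), the Month 24 standard error is about 0.79-0.92 of the true one. The 0.041 test then runs at about 0.06-0.10, and coverage is about 88-93%. The Month 1 standard error is about 1.1-1.6 times the true one, so inference there is conservative. These sizes come from assumptions, not from the SAP. No confirmatory conclusion depends on them. The unequal first visit gap is true but was not sized and adds little.

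**What to change.** In Section 8.3.2, change the fallback order to heterogeneous Toeplitz, heterogeneous AR(1), heterogeneous compound symmetry. Add that whenever the covariance is not unstructured, standard errors and tests come from the empirical (sandwich) estimator. The heterogeneous structures restore visit-specific variances; the sandwich also covers a wrong correlation pattern, including the one from unequal spacing.

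The cost is one sentence and an option in the procedure call; the primary analysis is untouched. There are two downsides. Sandwich standard errors are somewhat more variable, mainly in the small disease-stage subgroups of Section 8.7. They also do not remove bias from a misspecified covariance if dropout depends on outcome.
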